6.3.2 Maximum Reading Speed by MNRead

MNRead measures reading speed for each eye at visits V01 (Screening), V04 (Month 6), V06 (Month 12), V08 (Month 18), and V10 (Month 24).

Maximum reading speed (MRS) by MNRead at time points (baseline, Month 6, Month 12, Month 18 and Month 24) from Eligible Eyes and MRS greater than zero at baseline, will be summarized and analyzed in a similar way using MMRM described in [Section 6.2.2](#). The analysis model will use change from baseline in maximum reading by MNRead as the response variable, and will include treatment arm (ALK-001, placebo), pattern of FAF at the junctional zone of GA (banded/diffuse, focal/other/cannot grade), GA lesion multifocality (multifocal, unifocal/other/cannot grade), foveal status (foveal sparing, subfoveal/cannot grade) and time (year, categorical) as fixed effects, baseline GA lesion area and baseline maximum reading speed as covariates, time (year, categorical) \times treatment and baseline maximum reading speed \times time (year, categorical) interaction terms, subject and subject's eye (OD or OS) as random effects. A common unstructured covariance matrix will be used to model the within-subject errors, and the Kenward-Roger's (Kenward and Roger 1997) method will be used to estimate denominator

degrees of freedom. If the model fails to converge, alternative structures (heterogenous autoregressive (1), heterogeneous compound symmetry, autoregressive (1), or compound symmetry, in this order) will be considered.

The LS mean of the change from baseline in the maximum reading speed of Eligible Eyes, standard error, and 95% confidence interval (CI) will be estimated from baseline to Month 24 for each treatment arm. The estimated difference in change from baseline among the treatment groups along with the 95% CIs and p-value will be provided to test the significance of the treatment effect.

The observed values for the maximum reading speed of Eligible Eyes will be summarized by treatment group and visit. Summaries will present the descriptive statistics for baseline, absolute values and change from baseline data.

The mean change from baseline in the maximum reading speed of Eligible Eyes \pm the standard error, as well as the LS mean of the change from baseline in the maximum reading speed of Eligible Eyes \pm the standard error will be plotted over time by treatment group.

The categorical changes (improvements of ≥ 20 to <40 , ≥ 40 to <60 , ≥ 60 and minimal/no change (-20 to 20), worsening of ≥ 20 to <40 , ≥ 40 to <60 , ≥ 60) for Eligible Eyes will be summarized by treatment group and visit.

6.3.3 Binocular Reading Speed by IReST

Binocular reading speed, measured as correctly read words per minute, assessed by IReST is performed at visits V01 (Screening), V04 (Month 6), V06 (Month 12), V08 (Month 18), and V10 (Month 24).

Binocular reading speed by IReST at time points (baseline, Month 6, Month 12, Month 18 and Month 24) will be summarized and analyzed in a similar way using MMRM described in [Section 6.2.2](#). The analysis model will use change from baseline in binocular reading speed by IReST as the response variable, and will include treatment arm (ALK-001, placebo), pattern of FAF at the junctional zone of GA (banded/diffuse, focal/other/cannot grade), GA lesion multifocality (multifocal, unifocal/other/cannot grade), foveal status (foveal sparing, subfoveal/cannot grade) and time (year, categorical) as fixed effects, baseline GA lesion area and baseline binocular reading speed as covariates, time (year, categorical) \times treatment and baseline binocular reading speed \times time (year, categorical) interaction terms, subject as a random effect. A common unstructured covariance matrix will be used to model the within-subject errors, and the Kenward-Roger's (Kenward and Roger 1997) method will be used to estimate denominator degrees of freedom. If the model fails to converge, alternative structures (heterogenous autoregressive (1), heterogeneous compound symmetry, autoregressive (1), or compound symmetry, in this order) will be considered.

The LS mean of the change from baseline in the binocular reading speed, standard error, and 95% confidence interval (CI) will be estimated from baseline to Month 24 for each treatment arm. The estimated difference in change from baseline among the treatment groups along with the 95% CIs and p-value will be provided.

The observed values for the binocular reading speed will be summarized by treatment group and visit. Summaries will present the descriptive statistics for baseline, absolute values and change from baseline data.

The mean change from baseline in the binocular reading speed \pm the standard error as well as the LS mean of the change from baseline in the binocular reading speed \pm the standard error will be plotted over time by treatment group.

6.3.4 Visual function questionnaires

Visual function questionnaires are performed at visits V01 (Screening) or V02 (Day 1), V06 (Month 12), and V10 (Month 24).

6.3.4.1. Functional Reading Independence (FRI) Index Score

The FRI index score will be calculated per the scoring algorithm in the FRI Index user's manual.

FRI index score at time points (baseline, Month 12 and Month 24) will be summarized and analyzed in a similar way using MMRM described in [Section 6.2.2](#). The analysis model will use change from baseline in FRI index score as the response variable, and will include treatment arm (ALK-001, placebo), pattern of FAF at the junctional zone of GA (banded/diffuse, focal/other/cannot grade), GA lesion multifocality (multifocal, unifocal/other/cannot grade), foveal status (foveal sparing, subfoveal/cannot grade) and time (year, categorical) as fixed effects, baseline GA lesion area and baseline FRI index score as covariates, time (year, categorical) \times treatment and baseline FRI index score \times time (year, categorical) interaction terms, subject as a random effect. A common unstructured covariance matrix will be used to model the within-subject errors, and the Kenward-Roger's (Kenward and Roger 1997) method will be used to estimate denominator degrees of freedom. If the model fails to converge, alternative structures (heterogenous autoregressive (1), heterogeneous compound symmetry, autoregressive (1), or compound symmetry, in this order) will be considered.

The LS mean of the change from baseline in FRI index score, standard error, and 95% confidence interval (CI) will be estimated from baseline to Month 24 for each treatment arm. The estimated difference in change from baseline among the treatment groups along with the 95% CIs and p-value will be provided.

The observed values for FRI index score will be summarized by treatment group and visit. Summaries will present the descriptive statistics for baseline, absolute values and change from baseline data.

6.3.4.2. Visual Functioning Questionnaire 25 Item Version (VFQ-25)

The VFQ-25 total score will be calculated per the scoring algorithm in the user's manual.

VFQ-25 total score at time points (baseline, Month 12 and Month 24) will be summarized and analyzed in a similar way using MMRM described in [Section 6.2.2](#). The analysis model will use change from baseline in VFQ-25 total score as the response variable, and will include treatment arm (ALK-001, placebo), pattern of FAF at the junctional zone of GA (banded/diffuse, focal/other/cannot grade), GA lesion multifocality (multifocal, unifocal/other/cannot grade), foveal status (foveal sparing, subfoveal/cannot grade) and time (year, categorical) as fixed effects, baseline GA lesion area and baseline VFQ-25 total score as covariates, time (year, categorical) \times treatment and baseline VFQ-25 total score \times time (year, categorical) interaction terms, subject as a random effect. A common unstructured covariance matrix will be used to model the within-subject errors, and the Kenward-Roger's (Kenward and Roger 1997) method will be used to

estimate denominator degrees of freedom. If the model fails to converge, alternative structures (heterogenous autoregressive (1), heterogeneous compound symmetry, autoregressive (1), or compound symmetry, in this order) will be considered.

The LS mean of the change from baseline in the VFQ-25 total score, standard error, and 95% confidence interval (CI) will be estimated from baseline to Month 24 for each treatment arm. The estimated difference in change from baseline among the treatment groups along with the 95% CIs and p-value will be provided.

The observed values for the VFQ-25 total score will be summarized by treatment group and visit. Summaries will present the descriptive statistics for baseline, absolute values and change from baseline data.

6.3.4.3. Time Trade-Off (TTO) Questionnaire

Descriptive statistics for values and changes from baseline for time trade-off questionnaires will be summarized by treatment arm and visit.

6.3.4.4. Open-Ended Questionnaire

A listing of all answers on a per question per subject basis will be provided.

6.3.5 Incidence of CNV in the Study Eye

The number and percentage of subjects with incidence of CNV in the study eye, when the fellow eye has CNV at baseline, and 95% exact CI will be generated for each treatment arm. The proportion difference among the treatment groups, and the associated 95% Wald CI and Fisher's exact test p-value will also be provided.

6.4. Exploratory Efficacy Analyses

Descriptive statistics for values and changes from baseline for the continuous endpoints will be summarized by treatment arm and visit, and count and percentage for the categorical endpoints will be summarized by treatment arm.

- Changes in retinal sensitivity as measured by fundus-tracking microperimetry
- Incidence of CNV in the study eye, when the fellow eye has intermediate AMD at baseline
- Incidence of advanced AMD (CNV or GA) in the fellow eye, when the fellow eye has intermediate AMD at baseline

7.0. SAFETY ANALYSIS

Safety and tolerability are evaluated by AEs, SAEs, clinical laboratory test results, body weight, vital signs, 12-lead ECG findings, physical examination, and ocular exam and intraocular pressure (IOP). All analyses of the safety data are performed using the Safety Set. Descriptive statistics are presented by treatment group in the Safety Set. No formal statistical testing is performed for safety analyses.

7.1. Treatment Exposure and Compliance

Treatment exposure and compliance will be summarized by treatment arm, including the following:

- Duration of exposure (month), including number and percent of subjects with duration of exposure: < 1 month, >= 1 month, >= 3 months, >= 6 months, >= 12 months, >= 18 months
- Percentage of duration of exposure (%)
- Treatment compliance at Month 6, Month 12, Month 18 and Month 24, including numeric descriptive statistics and number and percent of subjects with compliance: < 70%, 70 - 90%, >90%

The treatment exposure and compliance data will be listed.

7.2. Adverse Events and Serious Adverse events

All reported adverse events (AEs) will be coded using MedDRA version 22.0 or higher following the MedDRA Term Selections Points to Consider.

An AE will be considered a treatment-emergent adverse event (TEAE) if it starts on or after the reference start date or if it starts before the reference start date but worsens on or after the reference start date, up to 28 days after last study drug administration.

The overall summary of TEAEs by treatment arm will include the numbers and percentages of subjects with at least one TEAE in the following categories:

- Any TEAE
- TEAE by Maximum Severity (evaluated by the investigator as Mild, Moderate and Severe)
- TEAE related to study drug (evaluated by the investigator as definitely, possibly, probably related)
- Treatment-emergent SAE
- Treatment-emergent SAE related to study drug (evaluated by the investigator as definitely, possibly, probably related)
- TEAE leading to study drug discontinuation
- TEAE leading to study drug interruption
- TEAE leading to study discontinuation
- TEAE leading to death (outcome = “Fatal”)

In addition, the numbers and percentages of subjects with at least one TEAE will be summarized by system organ class (SOC) and preferred term (PT) for the following categories:

- Any TEAE

- TEAE by Maximum Severity (evaluated by the investigator as Mild, Moderate, and Severe)
- TEAE related to study drug (evaluated by the investigator as definitely, possibly, probably related)
- Treatment-emergent SAE
- Treatment-emergent SAE related to study drug (evaluated by the investigator as definitely, possibly, probably related)
- TEAE leading to study drug discontinuation
- TEAE leading to study drug interruption
- TEAE leading to study discontinuation
- TEAE leading to death (outcome = “Fatal”)

Subjects who experienced multiple AEs within the same SOC or PT will only be counted once for that SOC or PT for that level of summarization. The maximum severity will be used in the summary of “TEAE by maximum severity” for subjects who experienced multiple AEs within the same SOC/PT.

Common TEAEs with at least 5% subjects in treatment group ALK-001 or with at least 2% subjects in treatment group ALK-001 and greater than placebo in percentage, will be summarized by PT respectively.

For each preferred term (PT), the number and percentage of subjects experiencing the event will be summarized by treatment arm and by duration of treatment at the time of first occurrence (categorized as <6 months, 6 – 12 months, >12 – 18 months, and >18 months). An estimated value and 95% confidence interval will be presented for the true rate of at least one AE or SAE by treatment arm.

Listings by subject will be provided for all AEs, SAEs, AEs leading to study discontinuation, and AEs leading to death, respectively.

7.3. Laboratory Tests

Laboratory tests, including laboratory parameters in chemistry, hematology, and lipids panel, are required at V01 (Screening), V04 (Month 6), V06 (Month 12), V08 (Month 18), V10 (Month 24), optional at all other visits.

Descriptive statistics for values and changes from baseline for laboratory results will be summarized by treatment arm and visit for chemistry, hematology, and lipids panel parameters listed in [Appendix 2](#).

The numbers and percentages of subjects for each laboratory parameter with quantitative laboratory values categorized as low, normal, and high, will be summarized by treatment arm and visit. Shift table in laboratory results (low/normal/high) from baseline to each post-baseline visit for each laboratory parameter will also be presented.

In accordance with the FDA guideline on Drug-Induced Liver Injury (*Drug-Induced Liver Injury: Premarketing Clinical Evaluation (2009) Section E2*)), following occurrences will be summarized by treatment arm and visit:

- Elevations greater than 3, 5, 10, and 20 times the upper limit of normal for AST, ALT, and either AST or ALT
- Elevations of bilirubin greater than 2 times the upper limit of normal
- Elevations of alkaline phosphatase greater than 1.5 times the upper limit of normal
- Elevations of ALT or AST greater than 3 times the upper limit of normal accompanied by elevations of bilirubin greater than 1.5 or 2 times the upper limit of normal.

The mean change from baseline \pm the standard error for laboratory parameters: ALT, AST, total bilirubin, triglycerides, HDL and LDL, will be plotted over time by treatment group.

All laboratory data will be listed.

There will be no imputation for missing laboratory results. For quantitative laboratory results reported as ' $<X$ ' or ' $\leq X$ ' or ' $>X$ ' or ' $\geq X$ ', a value of X will be used in the summary tables. The actual results as collected will be displayed in the listings.

7.4. Vital Signs

Vital signs collected include BMI (calculated from weight and height), body temperature, respiratory rate, heart rate, and blood pressure (systolic and diastolic), are required at V01 (Screening), V02 (Randomization / Day 1), V04 (Month 6), V06 (Month 12), V08 (Month 18) and V10 (Month 24), optional at V03 (Month 3), V05 (Month 9) and V07 (Month 15), V09 (Month 21).

Descriptive statistics for values and changes from baseline for each vital sign parameter will be summarized treatment arm and visit.

All vital sign results will be listed.

7.5. 12-Lead ECG

ECG measurements, including QT interval corrected by the Fridericia's formula (QTcF) and interpretation of ECG results (normal, abnormal not clinically significant, abnormal clinically significant), are required at V01 (screening), V06 (Month 12) and V10 (Month 24), optional at V05 (Month 9) and V07 (Month 15).

Descriptive statistics for values and changes from baseline for QTcF will be summarized by treatment arm and visit.

The numbers and percentages of subjects will be summarized by treatment arm and visit for QTcF >450 , >480 and > 500 msec and for QTcF change from baseline >30 and > 60 msec, respectively.

The numbers and percentages of subjects whose ECG interpretations by the investigator were normal, abnormal not clinically significant, and abnormal clinically significant will be summarized by treatment arm and visit.

All ECG results will be listed.

7.6. Physical Exam

A physical exam is conducted (sometimes optional) at visits V01 (Screening), V04 (Month 6), V06 (Month 12), V08 (Month 18) and V10 (Month 24). Results of the physical exam are considered normal, abnormal not clinically significant, or abnormal clinically significant.

A listing of all physical exam results will be provided.

7.7. Ocular Examinations and Intraocular Pressure

An ocular exam is performed (sometimes optional) at V01 (Screening), V04 (Month 6), V06 (Month 12), V08 (Month 18) and V10 (Month 24), as clinically indicated or based on routine care. Results of the ocular exam are either marked as (a) consistent with GA or (b) present with an abnormality that is inconsistent with GA, as assessed by the investigator. For cases where an abnormality inconsistent with GA was noted, clinical significance is evaluated by investigator.

Descriptive statistics for values and changes from baseline for intraocular pressure (IOP) by OD and OS will be summarized by treatment arm and visit.

The numbers and percentages of subjects whose ocular examination findings by the investigator were normal, abnormal not clinically significant, and abnormal clinically significant will be summarized by treatment arm and visit.

A listing of ocular examinations will be provided, including results marked inconsistent with GA and their clinical significance.

8.0. PHARMACOKINETIC ANALYSIS

Pharmacokinetics of ALK-001 over time when administered daily for 24 months will combine measures of absolute concentrations and percentage replacement with deuterated forms of vitamin A (as the sum of retinol and retinyl palmitate), retinol, and retinyl palmitate in plasma (required at all in-person visits except V02).

Pharmacokinetic measures include the following:

- Deuterated retinol as a fraction of total retinol
- Deuterated retinyl palmitate as a fraction of total retinyl palmitate
- Deuterated vitamin A as a fraction of total vitamin A, where vitamin A is computed as the sum of retinol and retinyl palmitate
- Other tested deuterated vitamin A metabolite(s) as a fraction of total vitamin A metabolite(s)
- Absolute concentrations (ng/mL) for each of the above analytes

Descriptive statistics for values and changes from baseline will be summarized for pharmacokinetic measures by treatment arm and visit (where a blood sample collection is performed).

The mean for pharmacokinetic parameters \pm the standard error will be plotted over time by treatment group.

The following method will be used to handle measurements that are below quantification limits (BQL):

- For subjects randomized to ALK-001:
 - At V01 (Screening) or V02 (Day 1), BQL deuterated values will be set to 0 and non-deuterated values will be set to the lower limit of quantification (LLOQ).
 - At visits other than V01 (Screening) or V02 (Day 1), all BQL values will be set to LLOQ.
- For subjects randomized to placebo:
 - BQL deuterated values will be set to 0 and BQL non-deuterated values will be set to LLOQ.

All PK analyses will be conducted in the PK Analysis Set using the above methods, on values provided by the lab while handling BQL values mentioned above, as well as on extrapolated values.

A listing of pharmacokinetic measures will be provided.

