## **1.4 PROTOCOL AMENDMENTS**

### **1.4.1 From Version 1.0 to Version 1.1**

Section	Change
Throughout the document	Subjects must be randomized between 2 and 4 weeks from V01
Throughout the document	No vitamin A-related quiz or information required to continue participation in the study.
Throughout the document	Diagnosis and treatment of CNV performed according to PI's standard of care.
Events Table (1.2)	
 
Changes in visit window to reflect study drug supply
 
V03 is optional
 
12-Lead ECG may be performed on either V05, V06 or V07
 
Visual Acuity, Low Luminance Visual Acuity and Reading Speed are optional on V02.
 
Vision Questionnaires are performed once a year.
 
Color Fundus Photograph performed at V01, then as clinically-indicated.
 
Fluorescence Angiography is performed at V01 and V10, and as clinically-indicated.
 
Microperimetry is optional at V02
 

Throughout the document	Syntactic changes and addition of clarifying information
Throughout the document	Subjects no longer expected to fast prior to a visit
Throughout the document	Subjects allowed to take the study drug before a study visit.
Exploratory Outcome Measures (Section 1.6.2)	Measuring incidence of GA in eyes with CNV added as exploratory measure.
Visual Acuity	EVA preferred to measure visual acuity; ETDRS is acceptable.
Exclusion Criteria (1.8.2)	Study eye refraction may not be higher than 6 diopters (positive or negative) if retinal imaging can be properly focused, as determined by PI.
Exclusion Criteria (1.8.2)	Exclusion of uncontrolled elevated IOP.
Dispensing Study Drug (1.9.12.3)	Subject may be discharged 30 minutes after intake of 1 st study drug.
Concomitant Medications (1.11)	Record use of retinoid medications up to 30 days prior to screening.
Concomitant Medications (1.11)	Subjects no longer prohibited from consuming saffron, curcumin, bilberry, "multivitamins for vision," resveratrol and CBD, however, the sponsor discourages their use.
Concomitant Medications (1.11)	Prescription eyedrops allowed for medical reason and according to approved label

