#### 1.5.8.2 Possible Benefits

- **Clinically-meaningful slowing of the growth rate of GA (Phase 3 section of protocol):** The study is powered to detect a 33% slowing in the growth rate of atrophic lesions. A survey of retinal specialists indicates that on average a ~20% slowing in the growth rate of GA would be considered clinically meaningful. Here, the study duration of 24 months was chosen to be long enough to measure a clinically meaningful slowing of 33%, while adequately evaluating the long-term safety and tolerability of ALK-001. The dose level was chosen so that 80% of vitamin A would be replaced with deuterated vitamin A after the first four weeks of treatment. Eighty percent replacement is expected to be therapeutic.
- **Slowing of the progression from GA to CNV (Phase 2 exploratory section of protocol):** The study is further powered to detect a 75% slowing in the progression from GA to CNV in the study eye, when the fellow eye has CNV. When the fellow eye has CNV, natural history data indicate that the incidence of CNV in the GA eye is approximately 10% per year, or ~20% after the 24 months of this study. Because vitamin A dimers trigger angiogenesis, stopping the formation of vitamin A dimers could slow the progression to CNV of the GA eye.
- **Slowing of the progression from CNV to GA (Phase 2 exploratory section of protocol):** Studies have shown that after 24 months of anti-VEGF therapy, ~17% of eyes with CNV will develop GA. Stopping the formation of vitamin A dimers could slow the progression to GA in the CNV eye. This is an exploratory endpoint.

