#### 1.7.2.8 *Pharmacokinetic Evaluations*

Plasma will be collected to measure compliance and further assess the pharmacokinetic profile of ALK-001, how it might be influenced by dietary vitamin A intake, how it fluctuates over a 2-year period as liver stores are turned over, and how the percentage of deuterated vitamin A in the blood might be linked to the progression of GA.

Metabolites of vitamin A measured in this study: ALK-001 is expected to replace existing, non-deuterated vitamin A. Total vitamin A in the plasma will be approximated by the sum of retinol + retinyl palmitate. Levels of deuterated retinyl palmitate peak 4 hours following administration of one ALK-001 dose then rapidly return close to baseline levels 24 hours post-dosing. Levels of deuterated retinol increase more slowly to peak 8-12 hours following dosing and decrease more slowly over time. Retinoic acid, another vitamin A metabolite with direct function on vision, will be measured. The absolute levels and percentage deuteration of retinol, retinyl palmitate and retinoic acid will also be measured. Percentages are calculated as the ratio between the deuterated analyte and the total amount of each analyte. Total amounts of each analyte will be calculated as the sum of the deuterated and the non-deuterated analyte. Absolute levels above the upper limit of normal may not indicate toxicity in the absence of clinical signs or other clinically meaningful laboratory abnormalities.

Levels of each analyte are expected to remain below the following upper limit of normal, determined based on a review of the literature:

Analyte (total deuterated + non-deuterated)	Approximate upper limit of normal
Retinol	1,500 ng/mL
Retinyl palmitate (random)	5,000 ng/mL
Retinyl palmitate (12+ hour after dosing)	500 ng/mL
Retinyl palmitate (24+ hour after dosing)	200 ng/mL
Retinoic acid (random)	5 ng/mL

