### **1.9.2 Timing of study drug intake**

- a) Subjects will be instructed to take one capsule per day, by mouth, at a time of their preference, preferably at the same time they take their other daily medications.
- b) Subjects will be instructed to take the study drug at approximately the same time each day.

- c) Time of usual study drug intake, duration elapsed since last study drug intake (at the time blood samples are collected during follow-up visits), and whether the capsule is taken before, after or during a meal should be recorded.

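### SAP 8.0 pools PK samples by visit regardless of hours since the last capsule, so composite percent deuterated vitamin A and the retinyl palmitate measures partly reflect sampling time

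*SAP*

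**What the plan says.** SAP 8.0 states that "Descriptive statistics for values and changes from baseline will be summarized for pharmacokinetic measures by treatment arm and visit", and plots the means over time by arm. It has rules for values below the quantification limit, but no window, stratum or covariate for hours since the last capsule. Two of its measures matter here:

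- the composite: "Deuterated vitamin A as a fraction of total vitamin A, where vitamin A is computed as the sum of retinol and retinyl palmitate";
- the retinol fraction, listed separately: "Deuterated retinol as a fraction of total retinol".

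Protocol 1.7.2.8 describes how differently the two components behave after a dose. For RP: "Levels of deuterated retinyl palmitate peak 4 hours following administration of one ALK-001 dose then rapidly return close to baseline levels 24 hours post-dosing". For retinol: "Levels of deuterated retinol increase more slowly to peak 8-12 hours following dosing and decrease more slowly over time". The same section gives approximate upper limits of normal for RP of 5,000 ng/mL (random sample), 500 (12 or more hours after dosing) and 200 (24 or more hours), against 1,500 for retinol.

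On sampling conditions, the version 1.1 change table (Protocol 1.4.1) records: "Subjects allowed to take the study drug before a study visit". Section 1.9.2 of version 1.0 told morning dosers to wait until after the blood draw; section 1.9.2 of version 1.1 has no such item. Section 1.12.29 of version 1.1 does not require fasting. Sections 1.9.2 and 1.12.30 have the time since last intake recorded when blood is taken.

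On the level sought, Protocol 1.5.8.2 says: "Eighty percent replacement is expected to be therapeutic".

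**The concern.** A visit mean built this way mixes samples taken a few hours after a capsule with samples taken a day after one. RP sits in both the numerator and the denominator of the composite, and by the protocol's own description it is the component that swings within a day. A sample near the RP peak is weighted towards the last capsule; a sample at 24 hours is weighted towards accumulated replacement. The RP fraction and the absolute RP and total vitamin A concentrations have the same dependence, and the protocol's RP limits cannot be applied to a mean pooled over dosing times.

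This matters because percent deuterated vitamin A is the protocol's PK outcome (1.6.2) and its plasma stand-in for retinal replacement (1.7.2.2). Section 1.7.2.8 also intends plasma to inform compliance and any link between percent deuteration and GA progression. If GA growth did not differ between arms, this measure would be consulted to judge whether replacement had been adequate. A composite raised by dosing on the visit day would make that judgement too favourable.

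**Working it through.** **The plan's own figure.** There is none to reproduce. The 80% level is a target, not a calculated quantity. The check is a mass balance.

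**Inputs**
- R, total retinol: 480 ng/mL (80 + 400, from the hypothetical table in Protocol 1.9.7.2), 1,000 (assumed, intermediate) and 1,500 (upper limit, 1.7.2.8).
- p, true deuterated fraction of retinol: 50%, assumed, and taken as unchanged by the capsule at the time of sampling.
- x, RP in the sample: 1,000 and 2,000 ng/mL. Assumed; the documents state no RP level after 14 mg.
- f, deuterated fraction of that RP: 95%, assumed, then varied.

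**Formula.** Composite % = (p × R + f × x) / (R + x)

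**Reading when the true retinol replacement is 50% (f = 95%)**

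| R (ng/mL) | x = 1,000 | x = 2,000 |
|---|---|---|
| 480 | (240 + 950)/1,480 = 80.4% | (240 + 1,900)/2,480 = 86.3% |
| 1,000 | (500 + 950)/2,000 = 72.5% | (500 + 1,900)/3,000 = 80.0% |
| 1,500 | (750 + 950)/2,500 = 68.0% | (750 + 1,900)/3,500 = 75.7% |

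From a true 30%, the readings are 73.9% and 82.4% at R = 480, 62.5% and 73.3% at R = 1,000, and 56.0% and 67.1% at R = 1,500.

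**RP needed for a true 50% to read 80%.** x = R × (0.80 − 0.50) / (f − 0.80)

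| f | R = 480 | R = 1,000 | R = 1,500 |
|---|---|---|---|
| 100% | 720 | 1,500 | 2,250 |
| 95% | 960 | 2,000 | 3,000 |
| 90% | 1,440 | 3,000 | 4,500 |

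All lie below the 5,000 ng/mL random-sample limit and above the 200 ng/mL limit for 24 or more hours. If f is 80% or less, a true 50% cannot read above 80% at any RP level.

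**Is 12 hours late enough?** Put RP at its 12-hour limit of 500 ng/mL, with f = 95% and R = 480. A true 50% reads (240 + 475)/980 = 73.0%. A true 65% reads (312 + 475)/980 = 80.3%. Deuterated retinol itself peaks at 8 to 12 hours, so the start of that window is not a trough for retinol either.

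**Is 24 hours late enough?** Put RP at its 24-hour limit of 200 ng/mL, fully deuterated. The composite reaches 80% only if p is at least 0.80 − 0.20 × 200/R, which is 71.7% at R = 480, 76.0% at 1,000 and 77.3% at 1,500. Only subjects already near the level would cross it. Some inflation remains: with f = 95% and R = 480, a true 50% would read (240 + 190)/680 = 63.2%. That is a reason to prefer the retinol fraction.

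**The case against.** Most of the protection is arguably already in place. SAP 8.0 lists the deuterated retinol fraction first and summarises it by visit, so a composite inflated by visit-day dosing would stand visibly above it in the same tables. The SAP sets no 80% cut-off and makes no PK-based adherence classification. SAP 7.1 reports exposure and compliance separately, and the protocol takes capsule counts. PK enters no primary or key secondary analysis. SAP 8.0 plans no comparison with the time-dependent limits, and Protocol 1.7.2.8 says values above them may not indicate toxicity without clinical signs.

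All of that stands, and it limits the consequence. It does not remove the defect: SAP 8.0 gives the retinol fraction no priority over the composite, and neither is shown against a variable the sites were asked to record.

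A reader might go further and infer that one capsule on the visit day does lift a poorly adherent subject above 80%. The documents do not support that as a finding. They give no RP level after 14 mg, and the 5,000 ng/mL figure is a literature-based upper limit rather than an observed value. The 95% deuteration is an assumption, and 480 ng/mL comes from a table labelled hypothetical. At R of 1,000 to 1,500 ng/mL, a true 50% reads 68.0% to 80.0%, at or below the level throughout. The figure in version 1.0, section 1.5.7.3, that plots the composite over 24 hours after a first 14 mg dose would bear directly on this, but its curve is not in the text available.

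**Conclusion.** The omission is established from the documents: PK samples are pooled by visit, hours since dose are recorded but unused, and version 1.1 permits pre-visit dosing. The direction also follows from the protocol's kinetics. Version 1.0, section 1.5.7.3 (superseded text), likewise describes an extra dose at steady state raising percent deuteration for a few hours, with a return by 24 hours.

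The size is not established. Under the assumed RP of 1,000 to 2,000 ng/mL at 95% deuteration, the composite overstates a true 50% by 18 percentage points (68.0 − 50, at R = 1,500) to 36 (86.3 − 50, at R = 480). Whether 80% is crossed depends on R, RP and f, and none of these has an observed post-dose value in the documents. The calculation also ignores any movement in the retinol fraction after the capsule.

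The effect falls on the composite, the RP fraction, absolute RP and total vitamin A, and much less on the slower-moving retinol fraction. It bears on descriptive PK and on how an efficacy result is explained, not on the efficacy tests.

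**What to change.** In SAP 8.0:

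1. List hours since last dose beside each PK value.
2. Summarise the composite, the RP fraction and the absolute concentrations by recorded time since dose (under 12 h, 12 to under 24 h, 24 h or more), within arm and visit where counts allow. Show the retinol fraction the same way.
3. State that any claim about 80% replacement, or any reading of adherence from PK, rests on the deuterated retinol fraction, or on the composite only from samples taken about 24 h or more after dosing. A 12-hour threshold should not be used for this.

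This changes the analysis text only; no dosing instruction is involved. It costs a few sentences and one variable the protocol already has recorded. The downside is smaller counts in each time-since-dose cell, so some visits may have to be combined.
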